15. EFFICACY ANALYSES

Investigator assessments of best overall response (BOR), ORR, PFS and OS will be summarized and listed for the ITT population. PFS and OS at weeks 24 and 56 will also be summarized.

15.1. OBJECTIVE RESPONSE RATE AND DURATION OF RESPONSE

Best Overall Response (BOR)

The summaries of BOR will include number and percentage of subjects in each of these categories:

- Complete response (CR)

- Partial response (PR)
- Stable disease (SD)
- Progressive disease (PD)
- Not Evaluable (NE)
- Unknown/Missing

Confirmation of CR/PR is required at least 28 days after the initial CR/PR was first met. Subjects will be evaluated for response based on the following disease appropriate criteria:

- For CNS tumors, response will be assessed based on RANO (Wen PY, 2010).
- Solid tumors will be assessed based on RECIST version 1.1 (Eisenhauer EA, 2009).

Objective Response Rate

ORR is defined as the percentage of subjects achieving a confirmed CR or PR from the start of tazemetostat until PD or the start of subsequent anti-cancer therapy, whichever is earlier, according to the appropriate disease evaluation criteria.

Subjects with not evaluable, unknown or missing best response will be handled as non-responders, i.e. they will be included in the denominator when calculating the ORR.

For dose escalation, ORR (secondary endpoint) will be summarized by dose level and overall.

For dose expansion, ORR (primary endpoint) will be summarized by cohort and overall. An exact 95% binomial CI for ORR in each cohort and overall will be provided as well.

In addition, ORR will be summarized by dose level across the dose escalation and dose expansion phases and overall. For each dose level and overall, an exact 95% CI for ORR will be calculated.

Also, a subgroup analysis of ORR by prior radiotherapy (Yes vs No) will be performed for the expansion phase by cohort and overall, and for the entire study by dose level and overall.

A plot of the maximum percent tumor reduction from baseline in target lesions for each subject will be provided.

Duration of Response

DOR will be calculated only for subjects with a confirmed CR or PR. DOR is defined as the interval of time from the first documented evidence of confirmed CR or PR until the first

documented PD or death due to any cause, whichever occurs first.

DOR censoring rules will follow those of the PFS analysis defined in **Table 3** below.

DOR will be analysed using Kaplan-Meier methods for each dose level within and across study parts, cohorts (if more than one) and overall. The median DOR, first quartile, and third quartile will be presented. The associated 2-sided 95% CIs will be estimated using the Brookmeyer-Crowley method (Brookmeyer 1982).

Table 3: Date of Event or Censoring for DOR

Situation	Date of event or censoring	Outcome
Death or disease progression between planned disease assessments	Date of death or first disease assessment showing disease progression, whichever occurs first	Event
Subsequent anticancer treatment started before disease progression or death (without disease progression beforehand)	Date of last adequate assessment ¹ prior to start of subsequent anticancer treatment	Censored
Death or disease progression after missing two or more consecutively scheduled disease assessments	Date of last adequate assessment visit without documentation of disease progression before the first missed visit	Censored
Alive and without documented disease progression	Date of last adequate assessment	Censored

¹An adequate assessment is defined as a radiological assessment where CR, PR, or SD was determined

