The ORR is defined as the percentage of subjects achieving a confirmed CR or PR from the start of treatment until disease progression or the start of new anticancer therapy. The 80% confidence interval for ORR in each cohort and overall will be calculated.

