9.3 Replacement of Subjects

A subject will be replaced during dose escalation if the subject:

- Is removed from a cohort during Cycle 1 for reasons other than toxicity (opinion of the Investigator will be consulted) or
- Has an interruption in dosing during Cycle 1 of more than 14 days total.

Subjects will not be replaced during the Dose Expansion portion of the trial.

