14.4.1 Analysis of Primary Endpoint by Cohort

The ORR is defined as the percentage of subjects achieving a confirmed CR or PR (using disease-appropriate standardized response criteria) from the start of tazemetostat treatment until disease progression or the start of subsequent anticancer therapy. The calculation of ORR will utilize the Full Analysis set. All subjects who received at least one dose of tazemetostat will be included in the determination of ORR regardless of the number of efficacy assessments performed. Subjects with not evaluable or missing response will be treated as non-responders; i.e., they will be included in the denominator when calculating the percentage.

In Dose Expansion, the ORR will be summarized by cohort and overall. An exact 95% CI for ORR in each cohort and overall will be calculated.

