2	2	0	0	De-escalate
3	0	0, 1, 2	3, 2, 1	Stay
3	0	3	0	Escalate
3	1	0, 1, 2	2, 1, 0	Stay
3	≥ 2	Any	Any	De-escalate
4	0	0, 1, 2, 3	4, 3, 2, 1	Stay
4	0	4	0	Escalate
4	1	0, 1, 2, 3	3, 2, 1, 0	Stay
4	≥ 2	Any	Any	De-escalate
5	0	0, 1, 2, 3, 4	5, 4, 3, 2, 1	Stay
5	0	5	0	Escalate
5	1	0, 1, 2, 3, 4	4, 3, 2, 1, 0	Stay
5	≥ 2	Any	Any	De-escalate
6	0	0, 1, 2, 3, 4	6, 5, 4, 3, 2	Suspend
6	0	5, 6	1, 0	Escalate
6	1	0, 1, 2, 3, 4	5, 4, 3, 2, 1	Suspend
6	1	5	0	Escalate
6	≥ 2	Any	Any	De-escalate

DLT = dose limiting toxicity

The MTD will be determined based on the incidence of DLTs in Cycle 1, although toxicities occurring in subsequent cycles will also be reviewed. If serious toxicities are observed at the MTD in later cycles, a reduction of the MTD may be considered.

The Clinical Safety Review Committee (CSRC) convened on 06-Jul. 2017 to review safety and PK from subjects at the 1200 mg/m² dose level. No DLTs were observed at 1200 mg/m² dose level. Although the Rolling 6 statistical design supported the escalation to the next dose level of 1600 mg/m², elevated chloride levels were observed in 3 of 6 evaluable subjects in the 1200 mg/m² dose level, and at previous dose levels as well. As tazemetostat is formulated as a hydrobromide salt, it was considered that the hyperchloremia could be an artifact of elevations in serum bromide. Thus, bromide levels were evaluated in 2 of 5 subjects on active treatment and were found to be elevated, though without any associated clinical signs or symptoms of

neurologic toxicity associated with bromism. CCI

Given the occurrence of the elevated bromide levels, as well as PD data, a decision was made by the CSRC to proceed to the dose expansion phase of the protocol with the putative RP2D determined to be 1200 mg/m² BID dose level with the understanding that bromide levels as well as clinical signs and symptoms of bromide toxicity would be closely monitored in all newly and currently enrolled subjects receiving tazemetostat with guidelines for immediate dose reduction as indicated.

Dose expansion at MTD or RP2D:

Approximately 72 subjects will be enrolled into the dose expansion in the following cohorts:

- Cohort 1 – approximately 20 subjects with ATRT
- Cohort 2 – approximately 20 subjects with malignant rhabdoid tumors (MRT)/rhabdoid tumors of the kidney (RTK)/selected tumors with rhabdoid features
- Cohort 3 – approximately 20 subjects with INI-negative tumors as follows:
 - Epithelioid sarcoma

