3.2. CHANGES TO ANALYSES FROM PROTOCOL

- Section 14.5.4 of the protocol indicates that laboratory analytes will be summarized descriptively as value and change from baseline, as well as shifts from baseline (based on low, normal, high categorization) at each visit. To allow for more focused presentation of values most likely to represent a safety concern, laboratory analytes will be summarized as shift from the baseline to the worst post-baseline category (based on National Cancer Institute [NCI] Common Terminology Criteria for Adverse Events [CTCAE] v 4.03 severity grades).
- In the protocol, PFS is to be summarized using 90% and 95% CIs. However, to be consistent and following standard analyses, PFS will be summarized using % CIs.
- In the protocol, ORR is to be summarized using 80%, 90% and 95% CIs. However, to be consistent and following standard analyses, ORR will be summarized using 95% CIs. In addition, it was indicated that the 95% CI would be done only for expansion phase cohorts with at least 20 patients, however the 95% CI would be provided for all expansion phase cohorts.
- No subgroup analyses were planned in the protocol, however, to assess the possible effect of tazemetostat on previously irradiated lesions, a subgroup analysis of ORR by prior radiotherapy

(Yes vs No) will be performed for the expansion phase by cohort and overall, and for the entire study by dose level and overall.

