4.2. PRIMARY ANALYSIS

The primary analysis for each cohort of the study may occur separately when each cohort has at least met its primary objective (further described in Section 15.1). Details regarding the timing of the PK, PD, genetics, and cellular pharmacologic analyses will be described in detail under separate SAPs.

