4.4. SAMPLE SIZE

Dose Escalation: The sample size is not based on a statistical consideration. The number of subjects will be determined based in part on the number of dose escalations required to determine the protocol defined MTD and/or RP2D. It is expected that up to approximately 48 subjects will be enrolled with the "Rolling 6" dose-escalation design (subjects who discontinue in absence of a DLT prior to the completing of the DLT evaluation period may be replaced).

The MTD and RP2D are defined as the dose level below which >1 subject of 3 or ≥ 2 subjects of 6 experience a DLT on the dose-escalation portion of the study during Cycle 1. In the event that MTD is not reached, the RP2D will be that dose that results in a mean $AUC_{(0-24)}$ of at least 5900 ng•h/mL (~80% of the mean value observed after administration of 800 mg BID in adults) or provides biologic and/or clinical activity in subjects in this study.

Dose Expansion: The sample size for dose expansion (Cohorts 1 to 3) is based on the hypothesized improvement in ORR over historical rates. An ORR no higher than 5% would

have no clinical benefit over existing therapies; an ORR of 20% is considered of clinical interest. For each dose expansion cohort separately, using a one-sided test and targeting a Type I error rate of 10% and a Type II error rate of 20% requires 20 pediatric subjects to be enrolled per cohort, in Cohorts 1 to 3. To establish that the data support tazemetostat, at least 3 of 20 subjects will be required to have an objective response (i.e., an observed 15% ORR) within a cohort. Due to the discrete nature of the primary endpoint, this statistical test achieves a Type I error rate of 8% (i.e., probability of deciding for tazemetostat when the true ORR is 5%), and a Type II error rate of 21% (i.e., probability of deciding against tazemetostat when the true ORR is 20%). Twelve subjects were to be enrolled in dose expansion Cohort 4 to evaluate the PK of tazemetostat when administered as a tablet formulation to pediatric subjects. Sufficient information to describe the PK of tazemetostat was obtained after administration of tazemetostat tablets to 4 pediatric subjects. Therefore, Cohort 4 was closed to further enrolment. Approximately 72 subjects will be enrolled across the 4 Dose Expansion cohorts.

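### Does the rule of at least 3 responders in 20 have to be restated for the actual cohort size, with an 80% interval beside the 95% one?

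*SAP*

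**What the plan says.** SAP 4.4, like Protocol 14.2.1, tests each of Cohorts 1 to 3 separately. The null ORR is 5% or less, the rate of interest is 20%, and the test is one-sided with targets of 10% and 20% for the two error rates. The rule is that "at least 3 of 20 subjects will be required to have an objective response (i.e., an observed 15% ORR) within a cohort", with attained errors printed as 8% and 21%. Protocol 14.1.2 states the same hypotheses.

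The size is not fixed exactly. SAP 3.1 plans "approximately 20 subjects with ATRT" for Cohort 1, and Cohorts 2 and 3 are worded alike. On the denominator, Protocol 14.4.1 says: "All subjects who received at least one dose of tazemetostat will be included in the determination of ORR". Subjects without an evaluable response count as non-responders. Protocol 9.3 adds: "Subjects will not be replaced during the Dose Expansion portion of the trial".

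For reporting, SAP 15.1 says: "An exact 95% binomial CI for ORR in each cohort and overall will be provided as well". Protocol 14.4.1 also asks for an exact 95% interval, whereas the protocol synopsis says: "The 80% confidence interval for ORR in each cohort and overall will be calculated". SAP 3.2 notes that the protocol's levels differ and declares the choice: "to be consistent and following standard analyses, ORR will be summarized using 95% CIs". SAP 7 still mentions two-sided 80% and 90% intervals wherever a later section calls for them; SAP 15.1 calls for 95% only.

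**The concern.** Two things look wrong.

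First, the rule is written for one sample size, and the analysis may use another. SAP 4.2 allows a cohort's primary analysis once its primary objective is met and points to SAP 15.1 for what that means. SAP 15.1 defines ORR and its interval but gives no null, test or count. If a cohort ended at 23 or more, keeping the count of three would exceed the 10% limit. If the 15% in parentheses were carried over instead, 21 or 22 subjects would need four responders, so 3/21 or 3/22 would pass on one reading and fail on the other.

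Second, a 95% interval is not the counterpart of a one-sided 10% test. At exactly 3/20 the rule is met, yet the only planned interval contains 5%. A reader who took that interval as the test would in effect require four responders, and power at a true ORR of 20% would fall from 79.4% to 58.9%.

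**Working it through.** **Inputs.** From SAP 4.4: null 5%, alternative 20%, one-sided limit 10%, n = 20, cut-off 3. From SAP 15.1: exact 95% interval. Assumption: sizes other than 20 are illustrative, because the documents give no actual cohort sizes.

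**1. The plan's own figures.** With X binomial(20, p), P(X ≥ 3) = 1 − [(1−p)^20 + 20p(1−p)^19 + 190p²(1−p)^18].

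- p = 0.05: 1 − (0.3585 + 0.3774 + 0.1887) = 0.0755, printed as 8%.
- p = 0.20: 1 − (0.0115 + 0.0576 + 0.1369) = 0.7939, so the Type II error is 0.2061, printed as 21%.

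Both reproduce.

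**2. The same test at other sizes.** The cut-off is the smallest k with P(X ≥ k | n, 0.05) ≤ 0.10.

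| n | P(X ≥ 3) at 5% | Cut-off k | Power at k, ORR 20% | Count if 15% is carried over |
|---|---|---|---|---|
| 15 | 3.6% | 3 | 60.2% | 3 |
| 18 | 5.8% | 3 | 72.9% | 3 |
| 20 | 7.5% | 3 | 79.4% | 3 |
| 21 | 8.5% | 3 | 82.1% | 4 |
| 22 | 9.5% | 3 | 84.6% | 4 |
| 23 | 10.5% | 4 | 70.4% | 4 |
| 25 | 12.7% | 4 | 76.6% | 4 |

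Two responders would suffice at n = 10 (8.6%) but not at n = 11 (10.2%), and three suffice up to n = 22 (9.5%). So three is the exact 10% cut-off for every n from 11 to 22, and four is the cut-off from 23 to 35. The 15% reading differs from the test at 21 and 22, where it would lower power to 63.0% and 66.8%.

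**3. How far n can move.** Dropout after dosing does not move it: treated subjects stay in the denominator and are not replaced. Only enrolment can. The planned total is 20 + 20 + 20 + 12 = 72.

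**4. The intervals.** The lower limit L of an exact two-sided 80% interval for x of n solves P(X ≥ x | n, L) = 0.10. This tail probability rises with L, so L exceeds 5% exactly when P(X ≥ x | n, 0.05) is below 0.10. The 80% interval is therefore the test in another form. For the 95% interval the threshold is 0.025.

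- 3/20: tail probability 0.0755, between 0.025 and 0.10. The 80% interval (5.6% to 30.4%) excludes 5%; the 95% interval (3.2% to 37.9%) includes it.
- 4/20: tail probability 0.0159. The 95% interval (5.7% to 43.7%) excludes 5%.

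At n = 20 the rule and the 95% interval part company only at exactly three responders, an outcome with probability 79.4% − 58.9% = 20.5% when the true ORR is 20%.

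**The case for a change.** The best case for a change is that a primary decision rule should not be left to inference once responses are known, least of all in an open-label study with investigator-assessed response. Cohort sizes here can depart from plan: Cohort 4 closed after tablet PK from 4 subjects against 12 planned, while the total of about 72 was kept. If all the freed places went to Cohorts 1 to 3, they would average (72 − 4)/3 = 22.7, so the total alone does not rule out a cohort of 23. One sentence and one table column would remove the doubt.

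Part of this stands: no passage says how the rule applies away from 20. But no passage moves those places either, and each cohort is still stated at about 20. At 23 the excess over the limit is half a percentage point, and then only if the analyst keeps the count and disregards the 10% limit in the same paragraph. The 15% is introduced as a restatement of 3/20, so it does not compete with the test.

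The interval argument is weaker. The power loss belongs to a test that nobody has specified. An 80% column would change no decision and would partly undo a choice that SAP 3.2 discloses. The SAP 4.2 pointer concerns when cohorts may be analysed; the objective is to evaluate activity by ORR, which SAP 15.1 does define.

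New cut-offs would also not be free of cost. Protocol Table 1 already shows an ORR of 13% in 85 subjects of this study, at a data cut a year before the amendment on which the SAP rests. Thresholds written now could look informed by the data, even though they follow mechanically from the test.

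**Conclusion.** No change is needed. SAP 4.4 gives the hypotheses, the one-sided 10% limit, the count and correct error rates, and that is enough for an analyst to reach a sound decision. The stated count holds unchanged for any cohort of 11 to 22 treated subjects. Outside that range, applying the stated limit by exact binomial calculation at the actual size settles the cut-off (four from 23 to 35). The missing instruction is a detail that analysts fill in one obvious way; a clarifying sentence would be harmless but optional.

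The 95% interval is a valid, declared description of precision. At 3/20 it will contain 5% while the rule is met. That is the expected result of reporting at a stricter level than the test, not a conflict in the plan. The leftover 80% and 90% wording in the synopsis and SAP 7 is clerical, since SAP 3.2 says which level applies.

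This rests on cohorts ending near the planned 20. At 23 to 25, a fixed count of three would carry a Type I error of 10.5% to 12.7%.

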15.2. PROGRESSION-FREE SURVIVAL

- PFS per appropriate criteria will be analyzed and listed for the ITT population only for the dose expansion phase of the study. PFS is defined as the interval of time (in weeks) from the date of first dose of study drug and the earliest date of disease progression or death, from any cause. For subjects who progressed or died after an extended period without adequate assessment, PFS will be censored at their date of last adequate assessment prior to progression or death even if subsequent information is available regarding progression or death. An adequate assessment is defined as an assessment where the Investigator determined response is CR, PR, or SD. The date of response at that assessment will be used for censoring.
- For subjects who receive subsequent anticancer therapy prior to the date of documented progression or death, PFS will be censored at the last adequate assessment (i.e., last assessment of CR, PR or SD) prior to the initiation of that anticancer therapy.
- For subjects who do not progress or die, PFS will be censored at the date of the last adequate tumor assessment.

PFS censoring rules are defined in Table 4 below.

In dose expansion, PFS will be summarized by cohort and overall. PFS will be analysed using the Kaplan-Meier method. Median PFS, first and third quartiles and associated 95% 2-sided CIs, will be estimated using the Brookmeyer-Crowley method [Brookmeyer, 1982]. PFS at 24 weeks and 56 weeks along with the associated 2-sided 95% CIs, will be provided. Kaplan-Meier PFS curves also will be provided.

Table 4: Date of Event of Censoring for PFS

Situation	Date of Event (PD/Death) or Censoring	Outcome: Event (PD/Death) or Censored
No (or inadequate) baseline tumor assessments and the subject has not died	Date of Study Day 1	Censored
No post-baseline assessments and the subject has not died (if the subject has died follow the rules for death indicted at the bottom of the table)	Date of Study Day 1	Censored
Progression documented between scheduled visits	Date of assessment of progression ¹	Event
No progression (or death) and no new anti-cancer treatment documented	Date of last ‘adequate’ assessment of response ²	Censored
No progression (or death) and new anti-cancer treatment documented	Date of last ‘adequate’ assessment of response ² on or prior to starting anti-cancer therapy	Censored
New anti-cancer treatment started (prior to documented disease progression or death). ³	Date of last ‘adequate’ assessment of response ² on or prior to starting anti-cancer therapy	Censored
Death before first PD assessment (or Death at baseline or prior to any adequate assessments)	Date of death	Event
Death between adequate assessment visits	Date of death	Event
Death or progression after one missed visit (with 2 week window)	Date of last ‘adequate’ assessment of response ² prior to missed assessments	Censored

¹ The earliest of (i) Date of radiological assessment showing new lesion (if progression is based on new lesion); or (ii) Date of radiological assessment showing unequivocal progression in non-target lesions, or (iii) Date of last radiological assessment of measured lesions (if progression is based on increase in sum of measured lesions)

² An adequate assessment is defined as a radiological assessment where CR, PR, or SD was determined.

³ If PD and subsequent anti-cancer therapy occur on the same day assume the progression was documented first, e.g., outcome is progression and the date is the date of the assessment of progression). If anti-cancer therapy is started prior to any adequate assessments, censoring date should be the date of Study Day 1.

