- v. **Disease Assessment:** 18 F-DG-PET scan to be performed if clinically indicated at the Investigator’s discretion. It is not a required disease assessment.
- w. **Post-Treatment/Early Termination Visit:** A Post-Treatment/Early Termination visit will be conducted within 30 days (\pm 3 days) after last dose of tazemetostat; prior to the start of a new treatment or therapy; or if the subject's participation is terminated early. This may occur at the time of treatment discontinuation (e.g., at the visit at which the decision to discontinue treatment occurs) or up to 30 days after the final dose of study drug. AE and concomitant medication data must be collected for 30 days after the final dose of study drug, or until the start of new therapy. If subject is unable to return to the clinic for assessment of AEs this may be done by telephone as long as the study subject does not require laboratory and/or other assessments related to any new or ongoing AEs, in which case a clinical visit will be required. In the event of a continuing AE, the subject will be asked to return for follow-up until the AE has resolved or is deemed to be continuing indefinitely.
- x. **Follow-Up for Progression-Free Survival:** Subjects who discontinue study treatment for reasons other than disease progression will continue to have disease assessments, when possible, every 8 weeks until disease progression or death.
- y. **Follow-Up for Overall Survival:** Subjects who permanently discontinue study treatment will be followed (by phone, email, or clinic visit) for survival every 16 weeks until death, withdrawal of consent, or they are lost to follow-up. Survival follow-up will continue for 2 years for each subject or until 80% of subjects enrolled have died. All anticancer therapies will be collected (the Sponsor may choose to stop the collection of therapies after the first anticancer treatment). Additionally, AESI and subsequent anti-cancer therapy information will be collected throughout the survival follow up.

- z. **Annual Assessments:** Annual assessments will be conducted including to review for AEs of special interest, tumor response if PD has not been previously reported, and PK (see footnote “o”).
- aa. **Optional Chest Ultrasound:** An optional chest ultrasound may be performed at the Investigator’s discretion to monitor for early signs of CCI/T-ALL.

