14.4.2 Analysis of Secondary Efficacy Endpoints

In dose escalation, the ORR will be summarized by dose level and overall.

In addition, the ORR will be summarized by dose level across the dose escalation and dose expansion parts (including cohorts) and overall. For each dose level and cohort with at least 20 subjects and overall across the study, an exact 95% CI for ORR will be calculated.

Progression-Free Survival (PFS) is defined as the interval of time between the date of the first dose of study drug and the earliest date of disease progression or death due to any cause.

For subjects who progressed or died after an extended period without adequate assessment, the time of PFS will be censored at their date of last adequate assessment prior to progression or death even if subsequent information is available regarding progression or death. An adequate

assessment is defined as an assessment where the Investigator determined response is CR, PR, or SD. The date of response at that assessment will be used for censoring. Specific rules for identifying extended loss to follow-up or extended time without an adequate assessment are provided in the SAP.

For subjects who receive subsequent anticancer therapy prior to the date of documented progression or death, the time of PFS will be censored at the last adequate assessment (i.e., last assessment of CR, PR or SD) prior to the initiation of that anticancer therapy.

For other subjects who do not progress or die, the time of PFS will be censored at the date of the last adequate tumor assessment.

Overall Survival (OS) is defined as the interval of time between the date of the first dose of study drug and the date of death due to any cause. For subjects who do not die, the time of death will be censored at the date of last contact. Death due to any cause will be included.

Within each cohort and overall, PFS and OS will be calculated using the Kaplan-Meier method. PFS and OS at 24 and 56 weeks and overall along with the associated 95% CIs will be provided. If there are a sufficient number of PFS events (i.e., progressions or deaths), median PFS, first and third quartiles and 90% CI, will be estimated using the Brookmeyer-Crowley method ([Brookmeyer, 1982](#)). If there are a sufficient number of deaths, median OS, first and third quartiles and 95% CI, will be estimated using the Brookmeyer-Crowley method. Figures and listings of PFS and OS will also be provided.

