Note: Stable doses of corticosteroids include subjects not on corticosteroids.

Disease progression (PD): PD is defined by any of the following:

- $\geq 25\%$ increase in sum of the products of perpendicular diameters of enhancing lesions compared with the smallest tumor measurement obtained either at baseline (if no decrease) or best response, on stable or increasing doses of corticosteroids
- significant increase in T2/FLAIR non-enhancing lesion on stable or increasing doses of corticosteroids compared with baseline scan or best response after initiation of therapy not caused by co-morbid events (e.g., radiation therapy, demyelination, ischemic injury, infection, seizures, post-operative changes, or other treatment effects)
- any new lesion; clear clinical deterioration not attributable to other causes apart from the tumor (e.g., seizures, medication adverse effects, complications of therapy, cerebrovascular events, infection) or changes in corticosteroid dose
- failure to return for evaluation as a result of death or deteriorating condition
- clear progression of non-measurable disease

Summary of RANO Response Criteria

Criterion	CR	PR	SD	PD
T1 gadolinium-enhancing disease	None	$\geq 50\%$ decrease	$< 50\%$ decrease but $< 25\%$ increase	$\geq 25\%$ increase ^a
T2/FLAIR	Stable or decrease	Stable or decreasing	Stable or decrease	Increase
New Lesion	None	None	None	Present
Corticosteroids	None	Stable or decreasing dose	Stable or Decreasing dose	NA ^b
Clinical Status	Stable or increase	Stable or increase	Stable or increase	Decrease
Requirement for Response	All	All	All	Any

Abbreviations: CR, complete response; FLAIR, fluid-attenuated inversion recovery; NA, not applicable; PD, progressive disease; PR, partial response; RANO, Response Assessment in Neuro-Oncology; SD, stable disease (Wen, 2010).

^{a.} Progression occurs when this criterion is present.

^{b.} Increase in corticosteroids alone will not be taken into account in determining progression in the absence of persistent clinical deterioration.

CCI

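### The SAP says DOR censoring follows the PFS rules, yet it censors PFS after one missed visit and DOR only after two or more, and the PFS row's 2-week window has no anchor

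*SAP*

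**What the plan says.** Protocol 14.4.2 censors PFS after an extended period without an adequate assessment and leaves the definition to the SAP: "Specific rules for identifying extended loss to follow-up or extended time without an adequate assessment are provided in the SAP".

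SAP 15.2 repeats the principle without a number. It adds that the censoring applies even where a later progression or death is known, and then states "PFS censoring rules are defined in Table 4 below". The last row of Table 4 reads "Death or progression after one missed visit (with 2 week window" and censors at the last adequate assessment before the missed assessments (plural). An earlier row, "Death before first PD assessment (or Death at baseline or prior to any adequate assessments", is an event on the date of death.

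SAP 15.1 states "DOR censoring rules will follow those of the PFS analysis defined in" Table 3. Table 3 is the DOR table. Its row is "Death or disease progression after missing two or more consecutively scheduled disease assessments", with no 2-week window.

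Tumor assessments are due every 8 weeks, within 3 days (Protocol Table 11, footnote u). Children who stop treatment without progression "will continue to have disease assessments, when possible, every 8 weeks until disease progression or death" (footnote x). PFS at 24 and 56 weeks is a named secondary endpoint for each expansion cohort (SAP section 2), estimated by Kaplan-Meier with 95% intervals.

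**The concern.** The protocol hands one question to the SAP: how long a gap makes a later progression or death uncountable. The SAP gives two thresholds while saying that the endpoints share one. The PFS threshold also cannot be programmed as it stands, because the 2 weeks are not counted from any stated date.

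The row matters because it acts only on children who later progress or die. A child who misses a scan and is stable at the next one stays in the analysis; a child who misses a scan and has progressed at the next one loses the event. That censoring is linked to outcome. In an open-label trial, choosing a reading after the data are known would be a post-hoc choice affecting a named endpoint.

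**Working it through.** **1. The plan's own figures.** The plan states no PFS or DOR rate, event count or power. Its only design figure is the ORR rule of at least 3 responders in 20. Exact binomial: P(X ≥ 3 | 20, 0.05) = 0.0755 and P(X ≤ 2 | 20, 0.20) = 0.2061, which round to the stated 8% and 21%. This point does not touch that rule.

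**2. A progression after one missed scan.** PR at week 8, confirmed at week 16, week-24 scan missed, PD at week 32. The gap since the last adequate scan is 32 − 16 = 16 weeks.
- Table 3 (DOR): one scan missed, so an event, with DOR = 32 − 8 = 24 weeks.
- Table 4, limit 8 + 2 = 10 weeks: 16 > 10, so PFS is censored at week 16.
- Table 4, limit 2 × 8 + 2 = 18 weeks: 16 < 18, so a PFS event at week 32.

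On the 10-week reading the same scan ends the response but is not a progression for PFS.

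**3. A death after a missed scan.** SD at week 8, week-16 scan missed, death at week 20; the gap is 12 weeks. The death-before-PD row gives an event at week 20. The last row, on the 10-week reading, gives censoring at week 8. An 18-week limit removes this conflict but not the overlap: with week 24 also missed and death at week 28, the gap is 20 weeks and both rows apply again.

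**4. Effect on landmark PFS.** The documents give no missed-scan rate, so every input here is an assumption: exponential time to progression, scans every 8 weeks ± 3 days, scans missed at random, 104 weeks of follow-up, and a PD found after a missed first scan kept as an event. The same simulated children (at least 200,000 per scenario) were coded under each rule. The entries are 56-week PFS under the 10-week reading minus PFS under the two-or-more rule, in percentage points; repeat runs agree to about 0.2 point.

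| Median PFS | 5% missed | 10% missed | 20% missed |
|---|---|---|---|
| 8 weeks | +0.1 | +0.1 | +0.3 |
| 16 weeks | +0.8 | +1.6 | +3.2 |
| 24 weeks | +1.5 | +2.8 | +5.5 |

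At median 24 with 10% missed, 56-week PFS goes from 20.7% to 23.5% and 24-week PFS from 51.2% to 51.9%. Over medians of 8 to 32 weeks the 24-week shift runs from about −1 to +1.6. Its sign varies because early censoring removes events but also shrinks the risk set at the scans in between. The 18-week reading matches the two-or-more rule to within 0.05 point.

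**5. No adequate post-baseline scan.** For a PD found after a missed first scan, the last row has no adequate post-baseline assessment to censor at. Table 4 uses Study Day 1 in other such cases but does not say so here. Censoring these children on Day 1 would raise the largest shifts over the same range of medians to about +9 points at 56 weeks and +5 to +6 at 24.

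**6. Scale.** The 95% half-width for 20 children is about 1.96 × √(p(1 − p)/20): 0.219 at p = 0.50 and 0.179 at p = 0.21, or about 22 and 18 points.

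**The case against.** **The thresholds may not differ.** A reader might infer that the SAP has settled on two different rules. The text does not go that far. If the window means two scan intervals plus 2 weeks, Table 4 agrees with Table 3, and the plural in the row's date column gives that some support. This stands: what is shown is a row with two readings, of which the literal one contradicts 15.1.

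**Precedence is not wholly open.** A reader might infer that nothing ranks the two death rows. SAP 15.2 and Protocol 14.4.2 both censor after an extended gap even when the death is known, which leans toward the last row. This also stands, but Table 4 does not carry it over and the length of the gap is the undefined part.

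**Longer scan intervals.** A reader might infer that 12- or 13-week scanning after Cycle 12 changes 56-week PFS for everyone. It does not: those intervals (Table 11 footnote u; Appendix 4) are for bone or brain scans in children with such disease at baseline, and footnote u keeps tumor assessments at 8 weeks. The 8-to-12-week schedule in Protocol 8.5.3 starts only one year after first response, or after one year of treatment with SD. No effect is claimed from applying longer intervals to all children.

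**Size.** Protocol Table 1 reports 13% ORR and 20% SD (defined as at least 32 weeks) in 85 children of this study. If all 33% were progression-free at 32 weeks, an exponential median would be 32 × ln 2 / ln(1/0.33) ≈ 20 weeks, so the 24-week row is on the generous side. That table pools doses and study parts. The size also depends on the miss model: with misses three times as likely in the 8 weeks before death, and deaths after a gap censored, 24-week PFS was 41.3% against 34.5% at 20% missed and a median of 24 weeks.

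**Direction of the repair.** SAP 15.1 has DOR follow PFS, so the documents' own direction would be to change Table 3. Choosing the Table 3 threshold is a recommendation, not something the documents require.

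**Conclusion.** The inconsistency is established on the text: 15.1 promises one set of rules, the tables state two thresholds, the reference to Table 3 is wrong for the PFS rules, and the window is unanchored. The overlap of the death rows is real, though the text of 15.2 leans toward censoring.

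The literal one-visit (10-week) reading tends to raise 56-week PFS, from a negligible amount at a median of 8 weeks to a few points at 16 to 24 weeks, with a small shift of either sign at 24 weeks. These sizes rest on assumed miss rates of 5-20% at random and on exponential progression.

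A reader might infer that the trial's conclusions are at risk. They are not: PFS here is descriptive with no decision rule, the shifts in the table lie inside the interval of a 20-child cohort, and the ORR rule and OS are unaffected. It should be fixed because two programmers could code the row differently and the repair is cheap.

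**What to change.** Before database lock, amend SAP 15.1 and 15.2:

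1. Use one threshold in Tables 3 and 4. Two or more consecutive missed scheduled assessments is preferable because it discards fewer known events. State it as a gap of more than twice the planned scan interval plus 2 weeks, counted from the last adequate scan (18 weeks for 8-week scans).
2. State which Table 4 row governs a death after missed scans, consistent with the text of 15.2.
3. Give the date to use when no adequate post-baseline scan precedes the missed ones.
4. Correct the table reference in 15.1.
5. Add one sensitivity analysis that counts every progression or death as an event.

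Separately, reconcile the 13-week bone and brain scan interval in Protocol Table 11 footnote u with the 12-week interval in Appendix 4, since the gap rule uses the planned interval for the children concerned.

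The cost is SAP wording and one extra table. The reported PFS may be slightly less favourable.
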